### **10.3.1 ABSORB IV Primary Endpoint**

#### **Primary Endpoint: TLF at 30-day Primary Endpoint**

TLF at 30-day will be tested for non-inferiority. This analysis will consist of ~2600 subjects in ABSORB IV.

The hypothesis test is designed to show non-inferiority of Absorb BVS to XIENCE for the TLF at 30 days with a one-sided alpha of 0.025. The null ( $H_0$ ) and alternative ( $H_A$ ) hypotheses are:

$$H_0: TLF_{\text{Absorb}} - TLF_{\text{XIENCE}} \geq \Delta_{\text{TLF}}$$

$$H_A: TLF_{\text{Absorb}} - TLF_{\text{XIENCE}} < \Delta_{\text{TLF}}.$$

$TLF_{\text{BVS}}$  and  $TLF_{\text{XIENCE}}$  are the 30-Day TLF rates in the Absorb BVS and XIENCE arms, respectively.  $\Delta_{\text{TLF}}$  is the non-inferiority margin for this powered primary endpoint.

The power calculation for the primary endpoint of TLF at 30 days is based on the following assumptions:

- The true 30-Day TLF rate is assumed to be 4.9% for both the Absorb BVS arm and the XIENCE arm
- One-sided alpha: 2.5%
- Non-inferiority margin ( $\Delta_{\text{TLF}}$ ): 2.9%
- Randomization ratio (ABSORB IV): 1 (Absorb BVS arm) : 1 (XIENCE arm)

- 1% loss to follow-up at 30 days

With the effective sample size 2574 (Absorb: 1287, XIENCE: 1287) at 30 days, the study has approximately 92% power to demonstrate non-inferiority of Absorb BVS to XIENCE using Farrington and Manning test.

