### ***10.3.2 Powered Secondary Endpoints***

#### ***Powered Secondary Endpoint 1: TLF through 1 year***

TLF at 1-year will be tested for non-inferiority. This analysis will consist of ~2600 subjects in ABSORB IV.

The hypothesis test is designed to show non-inferiority of Absorb BVS to XIENCE for the TLF at 1 year with a one-sided alpha of 0.025. The null ( $H_0$ ) and alternative ( $H_A$ ) hypotheses are:

$$H_0: TLF_{\text{Absorb}} - TLF_{\text{XIENCE}} \geq \Delta_{\text{TLF}}$$

$$H_A: TLF_{\text{Absorb}} - TLF_{\text{XIENCE}} < \Delta_{\text{TLF}}.$$

$TLF_{\text{Absorb}}$  and  $TLF_{\text{XIENCE}}$  are the 1 year TLF rates in the Absorb BVS and XIENCE arms, respectively.  $\Delta_{\text{TLF}}$  is the non-inferiority margin for this powered secondary endpoint.

The power calculation for the secondary endpoint of TLF at 1 year is based on the following assumptions:

- The true 1 year TLF rate is assumed to be 9.7% for both the Absorb BVS arm and the XIENCE arm.
- One-sided alpha: 2.5%
- Non-inferiority margin ( $\Delta_{\text{TLF}}$ ): 4.8%
- Randomization ratio (ABSORB IV): 1 (Absorb BVS arm) : 1 (XIENCE arm)
- 5% loss to follow-up at 1 year

With the effective sample size 2470 (Absorb BVS: 1235, XIENCE: 1235) at 1 year, the study has approximately 98% power to demonstrate non-inferiority of Absorb BVS to XIENCE using Farrington and Manning test.

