#### ***Power Secondary Endpoint 2: Angina through 1 year***

The Angina Powered Secondary Endpoint of percentage of patients who had angina within 1 year (excluding an angina blanking period of the index hospitalization or the first 7 days post PCI, whichever occurs first) will be tested for non-inferiority with reflex testing to superiority. This analysis will consist of ~2600 subjects in ABSORB IV.

The hypothesis test is designed to show non-inferiority of Absorb BVS to XIENCE for angina within 1 year with a one-sided alpha of 0.025. The null ( $H_0$ ) and alternative ( $H_A$ ) hypotheses are:

$$H_0: ANGINA_{\text{Absorb}} - ANGINA_{\text{XIENCE}} \geq \Delta_{\text{ANGINA}}$$

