## 10.4 Statistical Analyses

For binary variables such as TLF, TLR, and clinical procedure success, counts, percentages, and 95% confidence intervals will be calculated, and p-values may be presented for hypothesis generating purposes. Pearson's Chi-squared test or Fisher's exact test will be performed when

Confidential and Proprietary

Do not distribute or reproduce without the prior written permission of Abbott Vascular Inc.  
ABSORB III Randomized Control Trial Version 17.0 August 16, 2018.

appropriate. In addition, logistic regression will be performed to determine whether the baseline characteristics exhibit any trends in predicting TLF.

For continuous variables such as age, means, standard deviations, and 95% confidence intervals for the mean will be calculated and p-values may be presented for hypothesis generating purposes. For time-to-event variables, such as time to TLF, survival curves will be constructed using Kaplan-Meier estimates, and log rank test results may be displayed. Unless specified, analyses will be performed with pooled data across all study sites.

For further details refer to the statistical analysis plan (SAP).

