#### **10.4.1 Primary Endpoint Analyses**

The ABSORB IV Primary Endpoint of TLF at 30-day will be analyzed for the ITT (~2600 subjects of ABSORB IV) and the AT populations. The primary analysis will be based on the ITT population. The non-inferiority hypothesis testing will be performed using non-inferiority test by Farrington and Manning. Non-inferiority of Absorb BVS to XIENCE will be established if the p-value for the non-inferiority test is less than 0.025.

Details of the analyses for the primary endpoints can be found in the statistical analysis plan (SAP).

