#### **10.4.2 Powered Secondary Endpoint Analysis**

The ABSORB IV Secondary Endpoint of TLF at 1-year will be analyzed for the ITT (~2600 subjects of ABSORB IV) and the AT populations. The primary analysis will be based on the ITT population. The non-inferiority hypothesis testing will be performed using non-inferiority test by Farrington and Manning. Non-inferiority of Absorb BVS to XIENCE will be established if the p-value for the non-inferiority test is less than 0.025.

Analysis of the Angina Powered Secondary Endpoint of the percentage of patients with angina within 1 year will be based on the ITT population (~2600 subjects of ABSORB IV) and the AT population. The primary analysis will be based on the ITT population. The non-inferiority hypothesis testing will be performed using non-inferiority test by Farrington and Manning. Non-inferiority of Absorb BVS to XIENCE will be established if the p-value for the non-inferiority test is less than 0.025.

If the non-inferiority of Absorb BVS to XIENCE is demonstrated and the percentage is lower in Absorb BVS compared to XIENCE, a superiority test will be performed at the two-sided alpha 0.05 level.

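### The ABSORB IV protocol tests 30-day TLF, 1-year TLF and 1-year angina each for non-inferiority at one-sided 0.025 and states no testing order, so error across the three claims can reach about 5.9% to 6.6% unless the SAP sets one

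*Combined protocol and SAP*

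**What the plan says.** ABSORB IV Sections 10.3.1 and 10.3.2 set up three formal tests: "non-inferiority of Absorb BVS to XIENCE for the TLF at 30 days with a one-sided alpha of 0.025", "non-inferiority of Absorb BVS to XIENCE for the TLF at 1 year with a one-sided alpha of 0.025" and "non-inferiority of Absorb BVS to XIENCE for angina within 1 year with a one-sided alpha of 0.025". Section 10.4.1 gives the decision rule for the primary. Section 10.4.2 repeats it for each powered secondary: "Non-inferiority of Absorb BVS to XIENCE will be established if the p-value for the non-inferiority test is less than 0.025". Section 10.4.3 makes only the remaining secondaries descriptive, so both powered ones stay confirmatory.

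The secondaries are numbered, "Powered Secondary Endpoint 1: TLF through 1 year" and "Power Secondary Endpoint 2: Angina through 1 year", but nothing turns the numbers into a testing order, a condition or a split of alpha. The only conditional step is angina superiority, which follows angina non-inferiority (Sections 5.2, 10.3.2 and 10.4.2).

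The contents list a Section 10.4.7 on multiplicity with a bookmark error. In the body, 10.4.7 is early termination and the numbering then jumps to 10.4.10. ABSORB III does have a condition on its primary and a testing sequence (its Section 10.3.2), and a multiplicity section that points to the SAP (10.4.8). Both concern ABSORB III endpoints, and Section 11 of ABSORB IV brings in only ABSORB III Sections 11 to 17.

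The ABSORB IV Study Success paragraph in Section 10.1 defines success by the 30-day test alone.

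**The concern.** Followed literally, the text allows three non-inferiority claims, each tested at the full one-sided 0.025, with no rule to hold the error of the set. It also allows a secondary claim to stand when the primary has failed. The authors wrote a condition for angina superiority, so the lack of one elsewhere in the ABSORB IV text is noticeable. At stake is how far the 1-year TLF and angina claims can be read as confirmatory. The study-success claim is not at stake.

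**Working it through.** **Inputs (ABSORB IV 10.3.1 and 10.3.2)**

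| Test | Rate, both arms | Margin | N per arm | Stated power |
|---|---|---|---|---|
| 30-day TLF NI | 4.9% | 2.9 points | 1287 | 92% |
| 1-year TLF NI | 9.7% | 4.8 points | 1235 | 98% |
| Angina NI | 22.6% | 7 points | 1235 | 99% |
| Angina superiority | 17.7% vs 22.6% | none | 1235 | 86% |

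The correlation between angina and TLF is not in the documents. It is an assumption and is ranged below.

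**Step 1: the plan's own figures.** Farrington-Manning power is Φ((margin − 1.96·SE0)/SE1), where SE0 uses the restricted null rates and SE1 the planning rates. For 30-day TLF the restricted rates are 6.73% and 3.83%. This gives SE0 = √[(0.0673×0.9327 + 0.0383×0.9617)/1287] = 0.00880, SE1 = √[2×0.049×0.951/1287] = 0.00851, and Φ((0.029 − 1.96×0.00880)/0.00851) = 91.7%. The same method gives 97.9% and 98.6% for the other two non-inferiority tests; the chi-square test gives 85.9% for superiority. All four stated powers reproduce.

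**Step 2: correlations.** Every 30-day TLF is also a 1-year TLF, so nesting fixes the correlation of the two TLF statistics: √[0.049×0.903/(0.097×0.951)] = 0.69 at planning rates, and 0.70 at margin rates (7.8% vs 4.9%; 14.5% vs 9.7%). Angina and TLF overlap most if every TLF patient also has angina. The correlation is then √[0.049×0.774/(0.226×0.951)] = 0.42 with 30-day TLF and √[0.097×0.774/(0.226×0.903)] = 0.61 with 1-year TLF. At margin rates these are 0.44 and 0.62.

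**Step 3: any false non-inferiority claim, all three differences at their margins.** This is 1 − P(all three statistics below 1.96) from a trivariate normal.

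| Assumed angina-TLF correlation | Error |
|---|---|
| 0 | 6.6% |
| 0.3 | 6.3% |
| Largest attainable overlap | 5.9% |

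A simulation of 400,000 trials with the actual test statistic gave 6.4% with angina independent of TLF, and 6.2% at correlations of about 0.34 and 0.41. It runs slightly lower because the discrete tests fall a little under 2.5% each.

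**Step 4: milder cases.**
- Only the two TLF differences at their margins: 4.2%, counting non-inferiority claims only.
- Secondaries tested only after the primary passes, the primary certain to pass, both secondaries at their margins: 4.9% at correlation 0, falling to about 4.4% at the largest overlap.
- Study success: 2.5%, because it is one test.
- Angina superiority adds nothing in the least favourable case, since a false superiority claim there requires a false angina non-inferiority claim first.

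**Step 5: what a fixed sequence costs.** At planning rates, with angina-TLF correlation from 0 to the largest overlap, all three non-inferiority tests pass with probability about 90%. With angina at 17.7% vs 22.6%, both TLF steps and angina superiority all pass with probability 78.1% to 80.4% (80.7% if 0.5 is entered for both correlations). The current text gives about 86%.

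**The case against.** The strongest reply is that the hierarchy is in the SAP. ABSORB IV refers to an SAP for detail in several places (Sections 10.4, 10.4.1 and 10.4.3 among them), and ABSORB III shows that this sponsor keeps its multiplicity methods there. ABSORB III also uses the same unconditional wording for its primary decision rule, and its own Section 10.4.2 states no condition, although a sequence exists. The wording alone therefore does not prove that the tests are unordered. This stands, and it limits the claim to the protocol text. It does not remove the point: the ABSORB IV references are general, none mentions multiplicity, and the section that decides the secondary claims gives complete rules with no reference at all.

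It is also fair that the 5.9% to 6.6% needs all three excesses at their margins together. If only one endpoint is at its margin and the other two are truly non-inferior, false non-inferiority error is 2.5%. Nor do the ABSORB IV objectives tie these secondaries to label claims, as ABSORB III does for its own endpoints.

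Two stronger readings are tempting. A reader might count how often, at the planning rates, a secondary would be claimed after the primary is missed, and call that error. It is not: at those rates there is no true difference, so the secondary conclusion is correct. A reader might also infer that the trial's headline error is inflated. The Study Success paragraph rules that out.

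**Conclusion.** The point holds for the protocol text. Three confirmatory non-inferiority rules stand at one-sided 0.025 with no order, condition or split of alpha. In the least favourable case the chance of at least one false non-inferiority claim is about 5.9% to 6.6%. The range rests on an assumed angina-TLF correlation, from the largest overlap the protocol's rates allow down to 0. The simple sum of 7.5% is only an upper bound. Treating the primary as a precondition does not settle it, because two unordered secondaries still carry about 4.4% to 4.9%. The 4.2% for two TLF differences at their margins is not total error: if angina were truly equal, a false superiority claim could be added.

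The documents do not support saying that no hierarchy exists, because the SAP text was not available. Study-success error is 2.5%. This should be fixed, and it bears on the two powered secondary claims only.

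**What to change.** Restore the multiplicity section, repair the contents entry, and add to Section 10.4.2, for example: *Testing follows a fixed sequence. Each step is at one-sided 0.025 (two-sided 0.05 for superiority) and is taken only if every earlier step succeeded: (1) 30-day TLF non-inferiority; (2) 1-year TLF non-inferiority; (3) angina non-inferiority; (4) angina superiority. After the first failure the remaining tests are descriptive.* This is the order in which the protocol already numbers the endpoints, and it holds error across the set at one-sided 0.025. If the SAP already sets an order, cite that SAP section in 10.4.2 instead. Another pre-specified procedure with the same error control would also do.

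The cost is one paragraph and no patients. The downside is that an early failure blocks later claims, which takes about 5 to 8 points off the chance of reaching and passing angina superiority.

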#### **10.4.3 Secondary Endpoint Analyses**

Secondary endpoints other than the powered endpoints described above will be summarized descriptively for the ITT population (~2600 subjects of ABSORB IV). For further details refer to the statistical analysis plan (SAP).

#### ***10.4.4 Additional Analyses***

Adverse Events related to stent/scaffold thrombosis, vascular complications or bleeding complications, and their relation with antiplatelet therapies used in the trial will be investigated between the two treatment groups, if applicable.

For further details refer to the SAP.

#### ***10.4.5 Informational Endpoint Analyses***

Details on informational endpoint analyses can be found in the SAP.

#### ***10.4.6 Subgroup Analysis***

Pre-specified subgroups such as diabetes, sex, age will be examined. Further details can be found in the SAP.

#### ***10.4.7 Criteria for Early Termination of the Trial for Effectiveness***

No formal statistical rule for early termination of the trial for effectiveness is defined.

#### ***10.4.10 Procedures for Accounting for Missing, Unused or Spurious Data***

All analyses will be based on available data with missing data excluded. Any unused or spurious data will be noted as appropriate in the final report.

#### ***10.4.11 Pooling Strategy***

Details on pooling strategy can be found in the SAP.

#### ***10.4.12 Deviations from the Original Statistical Plan***

Any major changes to the statistical plan (available upon request) will be documented in an amendment to the statistical plan. Less significant changes to the planned analyses will be documented in the final report.

### **11. ADDITIONAL PROTOCOL INFORMATION**

Please refer to **section 11 - 17** of ABSORB III Protocol (Version 16.0, March 14, 2017) for relevant information on data access and handling, quality control, ethical consideration, publication policy, risk analysis and special population.

#### ***11.1 Direct Access to Source Data/Documents Addendum***

It is possible that during the duration of the trial, subjects may receive medical care from institutions other than the study site. In addition to collecting the informed consent from patients, the Sponsor strongly recommends that study sites obtain a medical release authorization from the subject to facilitate the collection of relevant medical information from non-study site institutions.

## 12. ABSORB-RESOLVE: REDUCTION IN ISCHEMIA WITH BIORESORBALE VASCULAR SCAFFOLDS—AN IMAGING SUB-STUDY TO ABSORB IV

### 12.1. *Background*

To date, no randomized controlled trial (RCT) has demonstrated the superiority of percutaneous coronary intervention (PCI) over medical therapy for the reduction of death or myocardial infarction (MI) in patients with stable coronary artery disease (CAD) [1,2]. Limitations of prior studies, however, have included excessively high rates of revascularization failure and incomplete coronary revascularization after PCI, and use of older generation stent technology (for example, only 2.7% of the COURAGE trial PCI patients received drug-eluting stents) [1,3].

Despite its negative primary clinical events outcome, COURAGE and numerous other RCTs have demonstrated that angina frequency and quality of life are significantly improved with PCI over medical therapy alone [4]. In COURAGE, a longitudinal assessment at 24 months observed PCI to improve health status compared to medical therapy, with two-thirds of patients undergoing PCI free of angina. The most prominent effect of PCI was noted for patients with either severe or frequent angina. Importantly, approximately half of subjects enrolled into the COURAGE study were asymptomatic or experienced minimal angina for a generally short duration of ~5 months, and PCI would be expected to be more effective in a more symptomatic group.

The symptomatic improvements with PCI in the COURAGE trial—despite the low utilization of drug-eluting stents—may be mechanistically explained by the COURAGE nuclear sub-study in which myocardial ischemia was evaluated by single photon emission computed tomography (SPECT) [5]. Abnormal single photon emission computed tomography (SPECT) findings have been strongly associated with adverse prognosis and worsened angina [6]. In the COURAGE nuclear sub-study, it was hypothesized that ischemia reduction would be greater for patients who were randomized to receive PCI over those receiving medical therapy alone [5]. Among 309 patients who underwent baseline and follow-up stress testing by SPECT, follow-up ischemia was assessed at 6-18 months (median 12 months). In PCI-treated patients, the mean amount of ischemic myocardium was reduced from 8.2% at baseline to 5.5% at follow-up—equating to a mean reduction of 2.7% — which compared favorably to the mean 0.5% reduction that was observed in the medical therapy alone arm ( $p < 0.001$ ). These findings are in direct accordance with several pivotal randomized trials including the Asymptomatic Cardiac Ischemia Pilot (ACIP) and SWISSI II studies, each of which demonstrated superior clinical outcomes with PCI compared to medical therapy alone in patients with documented ischemia [7-8].

#### 12.1.1. *Ischemia Assessment by SPECT*

Numerous non-invasive imaging tests exist for physiologic assessment of CAD, including echocardiography, cardiac magnetic resonance and myocardial perfusion imaging by either SPECT or positron emission tomography (PET) [9,10]. These modalities identify stress-induced wall motion abnormalities or regional myocardial perfusion defects as a surrogate for ischemia, and serve to identify individuals who may have severe coronary stenoses. Among the non-invasive stress modalities, myocardial perfusion imaging (MPI) by SPECT is performed most commonly, comprising ~90% of the more than 10 million stress imaging test performed in the

US annually [11]. MPI by SPECT determines the extent, severity and reversibility of myocardial ischemia with high performance [12]. In pooled analyses, the sensitivity and specificity of MPI to diagnose coronary stenosis is 85-90% and 70-75%, respectively. Further, the prognostic value of MPI is unsurpassed by other non-invasive tests, with risk of CAD events escalating exponentially with increasing magnitude of inducible hypoperfusion [6].

### 12.1.2. ***Coronary CT Angiography (CCTA)***

A major goal of imaging is to accurately evaluate the angiographic severity of luminal stenoses. Coronary CT angiography (CCTA) has recently emerged as an accurate non-invasive method for determination of obstructive CAD [13]. In three prospective multicenter studies, the diagnostic sensitivity of CCTA for patients with and without known CAD has ranged between 85-99%, with specificities ranging between 64-90% [14-16]. CCTA has been demonstrated to be particularly effective in excluding obstructive coronary stenosis and a normal CCTA is associated with a very low annual mortality rate of 0.13% [17].

However, there are limitations of CCTA, particularly as it relates to intracoronary stents [18]. Owing to blooming artifacts caused by metal, visualization of the coronary lumen within stents by CCTA is more challenging than evaluation of the native coronary arteries. Clinical studies published so far show low sensitivity to identify in-stent restenosis. The limited spatial resolution of CCTA, the type of stent, and stent diameter all contribute to limited clinical results.

Importantly, as blooming artifacts are absent in CCTA imaging of bioresorbable vascular scaffolds (Absorb BVS), the diagnostic performance of CCTA may be improved after Absorb BVS implantation [19]. The coupling of a non-invasive technique for evaluation of symptomatic or ischemic patients with suspected in-scaffold restenosis may be cost-effective compared to traditional evaluation of metallic stents [20].

### 12.1.3. ***CT Perfusion (CTP)***

Recent advances in technology now enable MPI by CT, a procedure termed CT perfusion (CTP) [21]. Multidetector CT systems can image in a dynamic mode, in which sequential images are obtained over a period of time to record the kinetics of iodinated contrast in the arterial blood pool and myocardium. George et al, using a 64-detector CT in a canine ischemia model, performed CTP during adenosine infusion [22]. They found strong correlations between the ratio of myocardial upslope and left ventricular upslope and microsphere-derived MBF. The authors replicated the study in humans with adenosine stress 64- and 256-row detector CCTA and CTP. In the human study, they calculated the transmural perfusion ratio (sub-endocardial attenuation / sub-epicardial attenuation), which had a significant inverse linear correlation with percent diameter stenosis on quantitative intracoronary angiography (ICA) [23]. Further, the combination of CTP and CCTA was 86% sensitive and 92% specific for identifying patients with atherosclerosis causing perfusion abnormalities when compared with the combination of ICA and SPECT-MPI as the gold standard.

In a prospective multicenter study of chest pain patients entitled the Combined Coronary Atherosclerosis and Myocardial Perfusion Evaluation Using 320 Detector Row Computed Tomography (CORE320) [24], CCTA with concomitant CTP was as effective as sequential SPECT-MPI and invasive angiography in identifying flow-limiting atherosclerotic lesions. The clinical utility of CTP may be particularly important in patients with a high coronary risk profile, known coronary artery disease, those with a high calcium score (e.g. >400 Agatston Units), or

Confidential and Proprietary

Do not distribute or reproduce without the prior written permission of Abbott Vascular Inc.  
ABSORB III Randomized Control Trial Version 17.0 August 16, 2018.

those with suspected in-stent restenosis in whom severe coronary calcification or artifacts prevent accurate quantification of coronary stenosis by CT angiography. In patients scheduled for percutaneous revascularization, information about both coronary lesion characteristics and myocardial segments with reversible ischemia or infarcts may be helpful to plan the procedure and provide prognostic information.

